Validation by primary data collection teams:

- Follow-up methodology at patient level: all hospitals will self-report the methods used to determine 30-day outcomes.
- Patient identification methodology: all hospitals will self-report the methods used to identify patients who fulfil the inclusion criteria.

Validation by independent teams:

- Case ascertainment: hospital records will be reviewed to identify patients fulfilling the inclusion criteria within a 2-week data collection period and comparing this to the actual number of cases submitted. This will be performed by individuals not involved in collecting the primary data. By comparing samples, a quantitative estimate of case ascertainment will be produced by the central data team.
- Data accuracy: a subset of collected variables will be validated by individuals who are independent of the primary data collection process. Following the “case ascertainment” stage, validators will be asked to provide data for a subset of variables, two patient variables, two operation variables, and two outcome measures.

Project Team Structure

Each registered centre must have a supervising consultant/attending to ensure adequate data quality. In the case that the hospital lead is a registrar/resident then they must recruit a consultant/attending to supervise the study. The hospital lead should also ensure that they recruit independent data validators (registrars/residents or consultants/attendings) to perform the data validation outlined in the section above.

For data collection, the hospital lead should recruit a “mini-team” of up to five local collaborators for each data collection period (**Table 1; page 15**). Medical students, doctors (non registrars/residents or consultants/attendings) and nurses can act as local collaborators and their participation is encouraged. The same “mini-team” can cover different time periods at each hospital if they wish to. Each team should include at least one qualified doctor to provide additional local support for participating medical students or nurses. Additional collaborators can be recruited to aid one-year follow-up data collection once the follow-up period begins (31st Jul 2024). A detailed specification of each role can be found below (see **pages 23-24**).

STATISTICAL CONSIDERATIONS

Primary Outcome Measure

The primary endpoint of this study is the compliance to pre-, intra-, and post-operative audit standards (see pages 9-10).

Secondary Outcome Measures

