Further prespecified subgroup analyses will be made by operative approach (open, laparoscopic and converted), and operative urgency (elective, emergency and delayed surgery). Audit standards (see pages 9-10) and site survey (Appendix C) will guide exploratory analysis into the global variation in the provision of cholecystectomy and available resources. However, it is acknowledged that some audit standards are designed for high-income settings and therefore their attainment will not be considered mandatory or a potential definitive measure of quality in global cholecystectomy.

Identification of hospital or surgeon-specific performance will not be reported. Following analysis, results will be fed back to participants at the centre level, but no other centres will be identifiable.

Based on previous GlobalSurg studies [14-16], GECKO is anticipated to include around 500 centres globally. With consideration to recent figures provided by previous collaborative studies [3,5] on cholecystectomy, a sample of approximately 15000 patients is anticipated. The recent multi-society practice guidelines on prevention of bile duct injury [8] advised that a study adequately powered to detect and report on bile duct injury would require at least 9000 patients.

DATA GOVERNANCE

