- All **GECKO** data will be collected and stored online through a secure server running the Research Electronic Data Capture (REDCap) web application. REDCap allows collaborators to enter and store data in a secure system. Collaborators will be given secure REDCap project server login details, allowing secure data storage on the REDCap database.

All data should be handled in accordance with national and local data governance policies. For instance, collaborators in the UK should seek their trust's Caldicott Guardian's permission to submit data to the REDCap system. **No data should be uploaded to REDCap prior to written approval from the Caldicott Guardian or ethical board.** No patient identifiable information should be uploaded or stored on the REDCap database without explicit permission from the trust's Caldicott Guardian. In other countries, no data should be uploaded to REDCap without local governance authorisation.

AUTHORSHIP

All authors will be credited in accordance with National Research Collaborative Authorship guidelines, and research outputs from **GECKO** will be listed under a single corporate authorship of GlobalSurg Collaborative, NIHR Global Surgery Unit [16,19,20].

Requirements for authorship on **GECKO** outputs include:

- Successful in obtaining all relevant local approvals for conduct of the **GECKO** study.
- Have completed the site survey.
- Successful data collection of at least one eligible patient per period for each site.
- Individual sites must also ensure:
 - A complete data set (>95% data points entered per record).
 - High case ascertainment (>90%, [see pages 16-17](#)).
 - All data has been uploaded by the specified database closure deadline.

All collaborators will be listed as PubMed-citable collaborators in accordance with the roles defined below (so long as the minimum requirements for authorship are met):

- **Writing Group:** A group of medical students, doctors and external advisory board members responsible for the overall scientific content, data analysis, and preparation of research manuscripts.
- **Steering Committee:** A core group of medical students and doctors who have overall responsibility for protocol design, project co-ordination, and data handling.
- **External Advisory Group:** A panel of international, cross-disciplinary field experts who are able to ensure contextual and scientific relevance of the protocol design, data fields and data interpretation.

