- Independent data validators:** A registrar/resident or a consultant/attending not involved with data collection whose role is to ensure adequate data ascertainment and data collection accuracy (see pages 16-17). The validator will be assigned to a 2-week data collection period at their local centre to validate. Data validation will occur following completion of data collection (including follow-up). After completing validation, the validator will send a summary of how many records were reviewed and error rates to the study management group.

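### Case ascertainment is set against a count of submissions, so wrongly included records can offset missed patients; one two-week window is also weak evidence for a site's >90% status

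*Protocol*

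**What the plan says.** Quality Assurance, Data Validation: people outside the primary data collection review hospital records for eligible patients in a two-week period, "comparing this to the actual number of cases submitted". It continues: "By comparing samples, a quantitative estimate of case ascertainment will be produced by the central data team". The section gives no formula, and it does not say whether the estimate is made per site or pooled. After this stage, validators supply six variables (two patient, two operation, two outcome) as a check on data accuracy.

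Authorship, role of the independent data validator: "The validator will be assigned to a 2-week data collection period at their local centre to validate". The validator then returns a summary of the number of records reviewed and the error rates. Project Team Structure asks the hospital lead to "recruit independent data validators (registrars/residents or consultants/attendings"), in the plural and without a number.

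Authorship, requirements for individual sites: "High case ascertainment (>90"%), with a cross-reference to the validation pages.

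Data Analysis & Sample Size: "GECKO is anticipated to include around 500 centres globally", and "a sample of approximately 15000 patients is anticipated". Table 1 lists eight two-week periods. Study Setting sets no minimum number of patients per centre.

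**The concern.** Two totals can agree without referring to the same patients. A site that misses an eligible patient and enters an ineligible one still scores 100%. The study is presented as a cohort of consecutive patients, and this check is its independent, quantitative test of that. A figure that can be too high, and that cannot show which patients were missed, is a poor test.

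A later analysis plan could not fully repair this. Matching has to be done at the site: REDCap holds no patient identifiers, and the validator is asked to return only a summary. If only counts come back, the missed patients cannot be identified centrally.

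The second issue is the size of the sample behind the site-level threshold. A proportion from one two-week window at an average centre may rest on very few patients.

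**Working it through.** The protocol states no sample size or precision for the ascertainment check, so there is no figure of its own to reproduce.

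**Offsetting errors.** Let E be the eligible patients in the window, M those missed and W the records wrongly included.

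- Count ratio = (E − M + W)/E
- True ascertainment = (E − M)/E
- Overstatement = W/E

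The documents give no rate for M or W. The values below are assumptions chosen to show the range.

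| E | M | W | Count ratio | True ascertainment |
|---|---|---|---|---|
| 4 | 1 | 1 | 4/4 = 100% | 3/4 = 75% |
| 10 | 2 | 2 | 10/10 = 100% | 8/10 = 80% |
| 30 | 6 | 0 | 24/30 = 80% | 24/30 = 80% |
| 30 | 6 | 2 | 26/30 = 86.7% | 24/30 = 80% |
| 30 | 6 | 4 | 28/30 = 93.3% | 24/30 = 80% |
| 30 | 5 | 5 | 30/30 = 100% | 25/30 = 83.3% |

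With no wrong inclusions the two measures agree. With 6 of 30 missed, four wrong inclusions carry the site over 90%; three give 27/30, which is exactly 90% and not above it.

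**Size of the window.** Inputs are 15,000 patients and 500 centres (Data Analysis & Sample Size) and eight periods (Table 1).

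- Patients per centre: 15,000/500 = 30
- Patients per centre per window, if all eight periods are covered: 30/8 = 3.75, about 4

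The number of periods a centre covers is an assumption, so it is varied below with 30 patients per centre held fixed. The pass probability is the exact binomial chance that the proportion found exceeds 90%, treating each patient as captured independently. The interval is the two-sided 95% Clopper-Pearson interval when every patient is found.

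| Periods covered | Patients in window | Needed to exceed 90% | Pass if true 95% | Pass if true 80% | 95% CI if all found |
|---|---|---|---|---|---|
| 8 | 4 | 4 | 81.5% | 41.0% | 39.8–100% |
| 4 | 8 (7.5 rounded) | 8 | 66.3% | 16.8% | 63.1–100% |
| 2 | 15 | 14 | 82.9% | 16.7% | 78.2–100% |
| 1 | 30 | 28 | 81.2% | 4.4% | 88.4–100% |

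For example, with 4 patients the pass probability is 0.95^4 = 0.815 or 0.80^4 = 0.410. With 10 or fewer patients a single miss fails the site, since 9/10 is not above 90%. With no misses at all, 29 patients are needed for a one-sided 95% lower limit above 90%, and 36 for a two-sided interval.

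**Pooled estimate.** One window per centre gives 500 × 3.75 = 1,875 patients. The 95% margin is 1.96 × √(p(1 − p)/1,875): 1.4 percentage points at p = 0.90 and 1.0 at p = 0.95, before allowing for clustering by site.

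**The case against.** The best reply is that a count-only comparison is one reading of the text. Validators identify individual patients, the estimate comes from comparing samples, and the six-variable accuracy check that follows must pair validator and submitted records. Some linkage is therefore implied in the same workflow. That is fair, but the protocol does not say that this linkage feeds the ascertainment figure, and its wording for that step refers to the number submitted.

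It can also be said that wrong inclusions are partly handled. Data Governance has the full dataset checked against the eligibility criteria and ineligible procedures removed, and the case report form records the data collection period. This stands as partial mitigation. The eligibility check is not tied to the ascertainment count, and it cannot reveal missed patients.

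Three stronger readings are tempting and are not supported:

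- A reader might infer that a site failing >90% ascertainment is dropped from the analysis and so biases the endpoints. The threshold is an authorship condition. Exclusion from analysis rests on more than 10% missing data (Study Setting) or, at the writing committee's discretion, on substantially incomplete data (Hospital Leads role).
- A reader might suppose that missed patients are mainly emergency, night-time or converted cases. Nothing in the document says which cases are missed.
- A reader might take the claim of consecutive entry to rest on this figure alone. It also rests on the hospital eligibility condition, daily review of lists and logbooks, and self-reported identification methods.

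**Conclusion.** The point holds as a weakness in a quality-assurance measure. Followed as written, the count comparison overstates ascertainment by W/E, and the document gives no information on the size of W. The 93% against 80% example shows what is possible; it does not estimate what will occur.

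The small-sample point holds for the site-level authorship rule. About 4 patients per window is an average derived from anticipated figures and assumes full coverage of all eight periods; actual centres will be larger or smaller. Use of a single window is the natural reading of the validator's role, but more than one validator per site is possible. Across the range of 4 to 30 patients, even complete capture leaves a two-sided 95% interval that includes 90%. One window is therefore weak evidence for a site's status, although at 30 patients it does separate true 95% from true 80% fairly well (81.2% against 4.4% passing).

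The same data, matched and pooled, would give a usable study-level estimate.

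**What to change.** - Define case ascertainment as the eligible patients independently found by the validator who match a submitted record, divided by all eligible patients the validator found.
- Do the matching only after the independent search is complete. The local list linking patient ID to REDCap ID, already required for one-year follow-up, can be used. It is held by a member of the data collection team, so the match should go through that holder.
- Report unmatched submissions separately as possible over-inclusion.
- Report the matched figure pooled overall, by human development index group and by operative urgency, with confidence intervals that allow for clustering by site.
- Do not let one two-week window alone decide whether a site meets the >90% authorship condition. Matching does not cure the small numbers.

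The cost is a little more validator time, using a list that already exists and record linkage that the accuracy check already needs. The downside for the sponsor is that reported ascertainment may come out lower than the count ratio.

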The secondary endpoints include:

- Rates of achieving a critical view of safety.
- Rates of different bailout procedures initiated when safe cholecystectomy is compromised.
- 30-day and one-year rates of textbook outcomes [2] for cholecystectomy, which covers: postoperative complications (Clavien-Dindo classification), intraoperative complications (including bile duct and vascular injuries), length of stay, readmission, mortality, and postoperative imaging or intervention.
- Unsuspected gallbladder cancer rates and their 30-day and one-year outcome rates, which includes: (1) complication rates (Clavien-Dindo classification); (2) time-to-recurrence rates (time from surgery to recurrence); and (2) revisional surgery rates (liver resection, bile duct resection and/or lymph node dissection).
- A description of the global variation in the availability of cholecystectomy services, training and sustainable practice.

Control of Bias and Confounding

Data will be collected on audit standards and confounding factors for risk-adjusted analyses. These include age, sex, body mass index, American Society of Anaesthesiologists (ASA) grade, and relevant comorbidities. Variables including operative urgency, operative contamination, and operative approach will also be collected. Without appropriately adjusting for risk factors, it is likely that any findings would be biased and unable to be appropriately analysed on an international scale. A full list of required data fields is available in **Appendix B**, and on the REDCap database.

Data Analysis & Sample Size

Variation across different international health settings will be tested using the human development index (HDI) countries [17] a composite statistic of life expectancy, education and income indices published by the United Nations. Initially, data will be reported using descriptive analyses. Comparisons between groups will be undertaken using appropriate parametric and non-parametric analyses. Multilevel logistic regression multivariate models will be constructed to account for case mix, with population stratification by hospital and country as random effects.

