Highest 30-day Clavien-Dindo (CD)	 0  I  II  IIIa (Radiological drainage?  Yes  No)  IIIb (Re-operation?  Yes  No)  IVa  IVb  V (Postop day of death: --)		Unplanned critical care admission  Yes (Length of stay: --)  No		Unplanned Re-imaging  Yes  No		 Yes  No	
30-day postoperative Complications (Tick all that apply)	 Surgical site infection (CD Grade:  I  II  IIIa  IIIb  IVa  IVb  V)  Pulmonary complications (CD Grade:  I  II  IIIa  IIIb  IVa  IVb  V)  Bile leak (CD Grade:  I  II  IIIa  IIIb  IVa  IVb  V)  Bleeding (CD Grade:  I  II  IIIa  IIIb  IVa  IVb  V)  Intra-abdominal collection (CD Grade:  I  II  IIIa  IIIb  IVa  IVb  V)  Acute pancreatitis (CD Grade:  I  II  IIIa  IIIb  IVa  IVb  V)							
Length of stay	-- days		Unplanned 30-day Readmission  Yes (Length of stay: --)  No					

Section 4: BDI data fields			

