2. Unplanned critical care admission - where critical care admission was not part of pre-operative plan	Yes / No If yes, please indicate length of stay in critical care: number of days (whole number)
3. Unplanned Re-imaging - where imaging in post-operative period (e.g.,	Yes / No If yes then tick all that apply: USS / CT / MRI / ERCP

CT, MRCP) was not part of pre-operative plan
	

4. 30-day postoperative complications (Select all that apply)
	
Surgical site infection (CD Grade* 0 / I / II / IIIa / IIIb / IVa / IVb / V) Postoperative pulmonary complications (CD Grade* 0 / I / II / IIIa / IIIb / IVa / IVb / V) Bile leak (CD Grade* 0 / I / II / IIIa / IIIb / IVa / IVb / V) Bleeding (CD Grade* 0 / I / II / IIIa / IIIb / IVa / IVb / V) Intra-abdominal collection (CD Grade* 0 / I / II / IIIa / IIIb / IVa / IVb / V) Acute pancreatitis (CD Grade* 0 / I / II / IIIa / IIIb / IVa / IVb / V) *For all of the above, please indicate the Clavien-Dindo grade associated with that complication

5. Length of stay
	
Whole number of days (Where discharge < 23 hours, enter 0. If the patient has not been discharged prior to the end of 30-day follow-up, enter '31')

6. Unplanned readmission within 30 days
	
Yes (Length of stay) / No

Bile Duct Injury (BDI) data fields
	
Required data (definition / comment)

1. BDI identified within 30-days of index cholecystectomy
	
Yes / No If yes: please fill in the rest of the data points below. If No: Was BDI identified within one-year of index cholecystectomy: Yes / No (if yes, then please fill in the rest of the data points below)

2. Presentation of BDI
	
Intraoperatively / Controlled bile leak from surgically placed abdominal drain / Abdominal pain due to uncontrolled bile leak / Obstructive jaundice or cholangitis / Intra-abdominal abscess or biloma

3. Days from index cholecystectomy to diagnosis
	
Number of days (0 = intraoperatively)

4. Bile duct injury grade
	
A / B / C / D / E1 / E2 / E3 / E4 / E5 (Strasberg Injury Grade: Appendix D for definition)

5. Concomitant vascular injury
	
Yes (Right hepatic artery / Common hepatic artery / Main portal vein / Right portal vein) / No

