3. TNM grade (AJCC 8th edition) (Appendix D for definition)	
T category: Tis / T1a (lamina propria) / T1b (muscularis) / T2a (peritoneal side) / T2b (hepatic side) / T3 / T4
 
N category: N0 / N1 (1-3 nodes) / N2 (>3 nodes)
 
M category: M0 / M1

4. Discussed at MDT	Yes / No
5. Adjuvant treatment	No / Chemotherapy / Radiotherapy
6. Revisional surgery completed	
Yes / No (not required) / No (unresectable tumour)
 
 • If yes, type of surgery (select all that apply): Liver resection (liver bed / one segment / two segments/ ≥ 3 segments) / bile duct resection / lymph node dissection • If yes, time from histology result to revisional surgery: Number of days (whole number)
7. Pathology results if revisional surgery	
Resection margin status: R0 / R1 / R2
 
Lymphovascular invasion: Yes / No
 
Perineural invasion: Yes / No
 
Resection margin definition: R0 = microscopically negative for residual tumor; R1 = microscopically margins still demonstrate the presence of tumor; R2 = macroscopically-visible disease remains post-surgery.

8. Recurrence on imaging at one year	
Yes / No
 
If yes, time from surgery to recurrence: number of days (whole number)

One-year Outcomes	Required data (definition / comment)
1. Highest one-year Clavien-Dindo (CD) Grade	
0 / I / II / IIIa / IIIb / IVa / IVb / V
 
If CD IIIa: Radiological drainage (yes / No)
 
If CD IV: Re-laparoscopy (yes / No)
 
If CD V (death): please indicate time from index cholecystectomy to death: number of days (whole number)

2. Readmissions	Total number of readmissions

3. One-year complications
(Select all that apply)

Surgical site infection (CD Grade* 0 / I / II / IIIa / IIIb / IVa / IVb / V)

Postoperative pulmonary complications (CD Grade* 0 / I / II / IIIa / IIIb / IVa / IVb / V)

Bile leak (CD Grade* 0 / I / II / IIIa / IIIb / IVa / IVb / V)

Biliary stricture (CD Grade* 0 / I / II / IIIa / IIIb / IVa / IVb / V)

Bleeding (CD Grade* 0 / I / II / IIIa / IIIb / IVa / IVb / V)

Intra-abdominal collection (CD Grade* 0 / I / II / IIIa / IIIb / IVa / IVb / V)

Acute pancreatitis (CD Grade* 0 / I / II / IIIa / IIIb / IVa / IVb / V)

*For all of the above, please indicate the Clavien-Dindo grade associated with that complication

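### The 30-day and one-year textbook outcome rates are not the same measure: general re-imaging is collected only to day 30, and the readmission field changes its definition

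*Protocol*

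**What the plan says.** The Protocol, Statistical Considerations, Secondary Outcome Measures, lists "30-day and one-year rates of textbook outcomes [2] for cholecystectomy, which covers: postoperative complications (Clavien-Dindo classification". The components are complications by Clavien-Dindo grade, intraoperative complications including bile duct and vascular injury, and then "length of stay, readmission, mortality, and postoperative imaging or intervention". No component is given a different window at one year.

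The data collection forms are organised by horizon:

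- **30 days.** Appendix B, 30-day Outcomes, item 3, reads "Unplanned Re-imaging - where imaging in post-operative period" and is answered yes or no, with a list of modalities and no date. In Appendix A, "Unplanned Re-imaging" sits in Section 3 (30-day outcomes). Readmission at this horizon is restricted to unplanned events and answered yes or no.
- **One year.** Appendix B, One-year Outcomes, has three items: "Highest one-year Clavien-Dindo (CD) Grade", "Total number of readmissions", and a list of complications with their grades. Section 6 of Appendix A has the same three. None of them records imaging.

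The section on Control of Bias and Confounding refers the reader to Appendix B for the full list of required fields. Data Governance says the dictionary was drawn up before data collection began.

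**The concern.** A composite reported at two time points is read as one measure observed for longer. Here one component is not observed for most patients after day 30, and another is defined differently at the two horizons.

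A patient whose only departure from a textbook course is unplanned imaging after day 30 would be counted as a success at one year. A patient readmitted only for a planned procedure could be counted as a failure at one year, although the same kind of event would not count at 30 days. The change between the two published rates would then mix real late events with differences in what the form asks.

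An analysis plan can redefine the composite, but it cannot recover imaging data that were never collected. For that reason the point belongs to the protocol and its case report form.

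**Working it through.** The protocol states no rate, power or sample size for this endpoint, so there is no figure to reproduce. The check is to match each named component to a field at each horizon.

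| Component (Secondary Outcome Measures) | 30-day field | One-year field |
|---|---|---|
| Complications by Clavien-Dindo | Yes | Yes |
| Mortality (grade V) | Yes | Yes |
| Bile duct injury | Yes | Yes |
| Other intraoperative complications | Recorded once, at surgery | Carried forward |
| Length of stay | Recorded once, entered as 31 if still an inpatient | Carried forward |
| Readmission | Unplanned, yes/no | Total count, planned and unplanned together |
| Intervention | Through grades IIIa/IIIb and their sub-items | Largely, through grade III and above and sub-items |
| Imaging | Unplanned, yes/no, undated | No general field |

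**Imaging after day 30.** Three fields can hold imaging later than day 30: the modality used to confirm a bile duct injury, staging investigations, and recurrence on imaging. The first is completed only if an injury is identified, the other two only if histology is malignant. Patients with an injury already fail the composite on that component, so the first field adds nothing to it. Everyone else has no imaging field after day 30.

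**Window without general imaging capture.** 365 − 30 = 335 days, and 335/365 = 91.8% of the year. This is a share of days, not of events.

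**Direction.**
- Imaging: an unrecorded failure can only turn a true failure into an apparent success, so this gap pushes the one-year rate up.
- Readmission: a count above zero includes planned admissions, for example for revisional surgery after unsuspected cancer. If any readmission counts as failure, this pushes the one-year rate down.
- Net: the sign is not determined by the documents.

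**Scale of the imaging part.** With N ≈ 15,000 (Data Analysis & Sample Size) and q the share of patients whose only failure is imaging after day 30, the number misclassified is N × q and the overstatement is q. The documents give no value for q, so these values are assumptions:
- q = 1%: 15,000 × 0.01 = 150 patients, 1 percentage point
- q = 3%: 15,000 × 0.03 = 450 patients, 3 percentage points
- q = 5%: 15,000 × 0.05 = 750 patients, 5 percentage points

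**A related mismatch in the intervention fields.** In Appendix B the one-year item attaches re-laparoscopy to grade IV. Section 6 of Appendix A (one year) attaches re-operation to grade IIIb, and the 30-day item in Appendix B attaches re-laparoscopy to IIIb. These three places must be reconciled, because the intervention component at one year depends on them.

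**The case against.** The strongest reply is that the gap is narrow, and much of this reply stands.

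- **Intervention is not lost.** Appendix D defines Clavien-Dindo III by the need for surgical, endoscopic or radiological intervention, and the one-year form records the highest grade with sub-items. In a yes/no composite a patient at grade III or above has already failed. A reader might infer that late intervention is invisible, but the documents do not support that.
- **Mixed time windows are not a fault in themselves.** Length of stay and intraoperative events occur once, and any one-year version must carry them forward.
- **The endpoint can be computed in some form.** A reader might conclude that no one-year textbook outcome can be delivered. That goes too far: a version whose imaging component stops at day 30 is computable if it is defined and labelled so.
- **Readmission is named without qualification in the endpoint.** The one-year count can be turned into yes/no, so this difference affects comparability and not computability.
- **The size may be small.** The bias needs late imaging with no readmission, no graded complication and no intervention. Grade I already covers any deviation from the normal course, so many late-imaged patients may fail on another item.

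What the reply does not answer is that the protocol states one definition for both horizons, lists imaging separately from graded complications, and then collects imaging for only one horizon. Imaging that leads to no treatment has no dependable place in a scale graded mainly by treatment required.

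**Conclusion.** The point holds in a limited form. As written, the forms yield a one-year rate that differs from its stated definition in two respects: general imaging is missing after day 30, and readmission is not restricted to unplanned events. The 30-day and one-year rates should not be compared or presented as the same measure.

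The two differences act in opposite directions and the documents do not fix the net effect. The only quantity that can be stated is the scaling for imaging alone: about 150 patients, or 1 percentage point, for each assumed 1% of about 15,000 patients who fail only on late imaging. A reader might be tempted to quote several hundred misclassified patients as an estimate, but nothing in the protocol supports any particular share.

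This concerns one secondary endpoint. The primary endpoint, compliance with audit standards, does not depend on it.

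**What to change.** Choose one of two routes.

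1. **Change the endpoint.** Restrict the full composite to 30 days, where every component has a field, and report the one-year components singly. Alternatively, keep a one-year composite but state explicitly that it excludes imaging after day 30, and label it as not comparable with the 30-day rate. This costs a sentence or two and no new data. The loss is small, because the Follow-up Period section justifies one-year follow-up by bile duct injury and unsuspected cancer, which have their own fields.
2. **Change the form.** Add one item to Appendix A, Section 6, and to Appendix B: unplanned re-imaging after day 30, with answers yes, no or not known. Record one-year readmissions as unplanned, to match the 30-day field. This costs a small amount of extra notes review at one year for each patient, which the high-volume centres will feel most.

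No separate intervention item is needed. Under either route, reconcile the grade to which re-laparoscopy or re-operation is attached in the one-year items of Appendix B, Section 6 of Appendix A, and the 30-day items of Appendix B.
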